## **8. STUDY PARTICIPANTS AND DEMOGRAPHICS**

### **8.1 Disposition of Participants and Withdrawals**

The numbers and percentage of participants randomized, completing the study, and withdrawing from the study, along with reasons for withdrawal, will be tabulated overall and by treatment group. The number and percentage of participants in each analysis population will be reported. This summary will be based on all participants who have data entered into the database.

### **8.2 Protocol Deviations**

Protocol deviations will be checked on complete data for all participants, determined during a (blinded) data review meeting before database lock, unblinding, and the final analysis.

Protocol deviations will be summarized by type and by treatment group for the Safety population. Protocol “violations” are not differentiated from deviations; instead, each deviation is identified either as “major” or “minor” depending upon its potential impact upon the integrity of the study data or the participant’s well-being.

Individual participants with protocol deviations will be listed.

### **8.3 Demographics and Other Baseline Characteristics**

Descriptive summaries of the demographic and other baseline characteristics will be completed for all participants in the safety population by treatment groups, unless otherwise specified.

Descriptive summaries of demographic and other baseline conditions will include:

- Demographics (age, gender, race/ethnicity, height, weight, body mass index (BMI), family status, education, presence of current MDE, current nicotine, alcohol and THC usage, and employment status). In addition to the safety population, these will also be repeated for all randomized participants and the mITT population.
- Psychiatric history (MINI 7.0.2)
- Clinician administered scales
  - C-SSRS-Baseline/Screening Version
  - CA-AF
  - CAPS-5 Assessment (Diagnostic version)

Other assessment’s baseline values will be reported with their respective follow-up measures.

Medical History will be coded using Medical Dictionary for Regulatory Activities (MedDRA) version 19.0 and summarized by System Organ Class (SOC) and Preferred Term using frequency counts by treatment group.

## 9. EFFICACY ANALYSES

### 9.1 Primary Efficacy Analysis Approach

The mean change from baseline in the total CAPS-5 score after 12 weeks of treatment in the TNX-102 SL 5.6 mg and placebo arms will be analyzed using a restricted maximum likelihood (REML) based repeated measures approach, including multiple imputation for missing values and accounting for the two-stage design. The model will include all participants in the mITT population. The dependent variable will be the observed change from baseline in total CAPS-5 score at each post-randomization visit.

#### 9.1.1 Primary Efficacy Analysis

An adaptive group sequential design will be performed by an independent third party statistical group [REDACTED] to cover an early efficacy stop, sample size adjustment, or futility stop; the final CSR analyses in all cases will be performed by [REDACTED] (the primary biostatistics vendor). To assure independence of the stage wise test statistics, the first stage population is defined as all participants available for efficacy analysis in the interim analysis. The second stage population is defined as all participants randomized after the interim cut-off and participants randomized prior to the interim cut-off, who were not available for efficacy analysis in the interim analysis.

Participants that drop out or reach Week 12 by the time of the interim cut-off will be included into the interim analysis. If the study continues until full planned recruitment, participants who were randomized prior to the interim cut-off, but did not drop out or reach Week 12 by the time of the interim cut-off, will be included into the second stage test statistic. Participants that were randomized after the interim cut-off will be included in the calculation of the second stage test statistic. Note that in every case, only participants that meet the mITT population criteria will be included.

If the study is stopped early for efficacy, participants who were randomized prior to the interim cut-off but did not drop out or reach Week 12 by the time of the interim cutoff will be offered an immediate transition into open label extension safety study (TNX-CY-P306) and will not be included in the efficacy analyses.

Data of different stages will be combined using the inverse normal method to test the null hypotheses that there is no difference in the change from baseline in CAPS-5 total score between TNX-102 SL and placebo treatment groups at Week 12:

$$Z_1 = \Phi^{-1}(1 - p_1)$$
$$\text{and } Z_2 = w_1 Z_1 + w_2 \Phi^{-1}(1 - p_2)$$

Where:

$Z_1$  = the Z statistic for the first stage

$Z_2$  = the combination test statistic at the end of the second stage

$w_i$  = the weighting applied for each associated Z statistic

$p_1$  = the first stage p-value

$p_2$  = the second stage p-value based on second stage participants

For maximum statistical efficiency, the weights are defined prospectively according to the square-root of the planned proportion of participants in the two stages, relative to the preplanned total enrollment of 550 participants, as  $w_i = \sqrt{0.5}$ . The calculation of these weights is fixed and will not be changed due to unblinded data and is hence in line with the draft guidance on adaptive design clinical trials (CDER, CBER, February 2010). In order to control the type-I error, adaptive changes of the stage wise sample sizes will not lead to changes of the weights (Lehmacher & Wassmer 1999).

A Mixed Model Repeated Measures (MMRM) analysis will be performed for the change from baseline in CAPS-5 total score to estimate the treatment difference at Week 12. The model will include all participants in the mITT population, and the dependent variable will be the observed change from baseline in total CAPS-5 score at each post-randomization visit. Covariates in the model will include the fixed categorical effects of treatment, site, sex, current tobacco use status, presence of current MDE, visit and treatment by visit interaction, as well as the continuous fixed covariates of baseline score and baseline score by visit interaction. An unstructured covariance matrix will be used to model the within-subject variance-covariance errors. The Kenward-Roger approximation will be used to estimate the denominator degrees of freedom. Should the unstructured model fail to converge, an autoregressive AR(1) covariance structure will be attempted, then finally compound symmetric should AR(1) not converge.

Missing data for participants in the mITT population will be imputed via multiple imputation (MI) (Carpenter, 2013; Mallinckrodt, 2013). Ten repeats of the imputation will be performed using Markov Chain Monte Carlo (MCMC) assuming non-monotone missing. Where the study medication was discontinued due to lack of efficacy, lost to follow-up, or to an AE, missing values will be imputed drawing from the baseline values, conditioned on the non-missing post-baseline values, of all participants in the mITT population under the assumption that they are missing not at random (MNAR); covariates will include site, sex, tobacco use, and presence of current MDE. If the study medication was discontinued for any other reason, values will be imputed within treatment group using MI under the assumption that they are missing at random (MAR) with covariates for site, sex, tobacco use, presence of current MDE, and the CAPS-5 score recorded at each time point (including baseline). The MAR approach will also be applied for sporadic missing values (prior to discontinuation).

The test statistic based upon the least squares (LS) mean treatment difference and associated p-value [redacted] will be presented for each stage. The study may stop early for success in the case where the critical boundary is crossed (see Section 5.7 of the ISAP). Given an early efficacy stop, the remaining participants will be offered an immediate transition into an open label extension safety study (Protocol No. TNX-CY-P306) and will not be included in the efficacy analyses;

likewise ongoing subjects will not be included in final efficacy analyses in the case of a futility stop.

In addition, the least squares means and 95% confidence intervals (CIs) will be calculated for the treatment difference between TNX-102 SL and placebo at each time point.

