13. STATISTICS

A full description of the statistical analyses to be performed at study completion will be provided in a Statistical Analysis Plan (SAP), which will be finalized prior to the interim analysis.

One interim analysis is planned (See [Section 13.6](#)) prior to the completion of the study. A full description of the interim analysis will be provided in an Interim Statistical Analysis Plan (ISAP), which will be finalized prior to the interim analysis.

Baseline will be defined as those values recorded closest to, but prior to administration of the first dose of study drug.

Unless otherwise noted, significance tests of treatment differences will be tested at the two-sided 0.05 level.

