### **3. OVERALL STUDY DESIGN AND PLAN**

This is a Phase 3, 12-week, randomized, multicenter, double-blind, placebo-controlled, fixed dose study that will investigate the efficacy and safety of TNX-102 SL 5.6 mg taken daily at bedtime for the management of military-related PTSD. This study is to be conducted at approximately 45 investigational sites in the United States.

The total duration of this study over 6 visits will be approximately 13-17 weeks, with 12 weeks of treatment duration and a variable length of screening. This study will consist of a Screening visit (Visit 1, Days -35 to -7), Randomization visit (Visit 2, Day 0), telephone visit (Visit 3, Week 2) and three monthly in-clinic visits (Visits 4, 5 and 6 at Weeks 4, 8, and 12).

Eligible participants who provide written informed consent to participate will have study assessments performed at Screening, including counseling regarding any required washout and instructions to refrain from use of excluded medications throughout the study.

The length of the pre-randomization screening period is variable (7 to 35 days) in order to accomplish wash-out of previous medications, where appropriate, and allow for return of clinical laboratory results necessary to confirm eligibility. At Visit 2, participants will return to the site for additional baseline assessments and randomization (Day 0), when, if they meet all study randomization criteria, they will be randomly assigned in a 1:1 ratio to receive placebo or TNX-102 SL 5.6 mg. A dynamic randomization procedure will be employed at Visit 2 to minimize trial-wide imbalances between the treatment groups for site, sex, current tobacco/nicotine use (yes/no) and presence (yes/no) of current Major Depressive Episode (MDE) based on the Mini International Neuropsychiatric Interview, Version 7.0.2 (MINI 7.0.2) conducted at Visit 1.

Participants will take the study drug sublingually daily at bedtime, starting on the day that they are randomized and continuing for 12 weeks. Participants will return to the study center for safety and efficacy assessments at Weeks 4, 8, and 12 (or early termination [ET]).

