## 5. SAMPLE SIZE DETERMINATION

The study is planned to enroll approximately 550 participants total in a 1:1 randomization, that is, 275 participants in each of the placebo and TNX-102 SL 5.6 mg groups.

The interim analysis will re-evaluate these assumptions and the IDMC may recommend a sample size increase.

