## **7. GENERAL ISSUES FOR STATISTICAL ANALYSIS**

### **7.1 General Statistical Methodology**

Descriptive summaries will be provided where appropriate for each of the primary and secondary variables. In general, tables will summarize data by treatment group and visit.

Baseline characteristic and safety tables will be completed for the Safety Population unless otherwise specified. Efficacy tables will be presented for the mITT Population.

Continuous, quantitative, variable summaries will include the number of participants (N) with non-missing values, mean, standard deviation (SD), median, minimum, and maximum.

Categorical, qualitative, variable summaries will include the frequency and percentage of participants who are in the particular category. In general, the denominator for the percentage calculation will be based upon the total number of participants in the study population for the treatment group unless otherwise specified.

Baseline values are defined as the last non-missing measurement prior to the first dose of study drug. Change from baseline will be defined as the post-baseline visit value minus the baseline value.

ET participants will only be followed if required to monitor an on-going adverse event or other condition.

Participants are not supposed to change study sites; however, should this be necessary to allow a participant to continue in the study, participants will be analyzed under the site where they were initially enrolled.

Study day after first dose is defined as assessment date – first dose date +1. Dates prior to first dose are defined as assessment date – first dose date. Note that the protocol refers to “Day 0”; for the purposes of the datasets and analyses, this would appear as day 1.

All analyses will be performed using Statistical Analysis System (SAS®) Software version 9.3 or later.

Alpha levels are discussed in [Section 7.1.1.2](#) below; unless otherwise noted, 95% confidence intervals will be presented for statistical tests.

Presence of current tobacco/nicotine use and MDE is recorded first in the Interactive Web Response System (IWRS) during screening for purposes of randomization stratification and, after randomization, transcribed into the electronic data capture (EDC) system (as part of substance use history and the results for the MINI). The source for tobacco/nicotine use MDE in all analyses and statistical models will be the EDC data and not the IWRS.

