## 9.2 Secondary Efficacy Analysis

### 9.2.1 Continuous outcomes

The analyses of continuous secondary endpoints will be analyzed using an MMRM model identical to the primary endpoint, however, there will be no multiple imputation applied. These endpoints will include:

- CGI-I score.
- Change from baseline in SDS total.
- Change from baseline in participants' quality of sleep using the PROMIS Sleep Disturbance scale.
- Change from baseline in the disruption of work/school activities assessed using the SDS.
- Change from baseline in disruption of social life/ leisure activities assessed using the SDS.
- Change from baseline in the disruption of family life/home responsibilities assessed using the SDS.
- Change from baseline in CAPS-5 Arousal and Reactivity (Criterion E).
- Change from baseline in CAPS-5 Intrusion symptoms (Criterion B).
- Change from baseline in CAPS-5 Negative Cognition and Mood (Criterion D).
- Change from baseline in CAPS-5 Persistent Avoidance (Criterion C).
- Change from baseline in CAPS-5 Sleep Disturbance (item E-6).
- Change from baseline in CAPS-5 Exaggerated Startle (item E-4).
- Change from baseline in CAPS-5 Reckless or Self-Destructive Behavior (item E-2).
- Change from baseline in CAPS-5 Depersonalization (item 29).
- Change from baseline in CAPS-5 Derealization (item 30).
- PGIC score.
- Change from baseline in BDI-II score.

The model will be changed to include the corresponding baseline value of the secondary endpoints instead of baseline CAPS-5. Randomized participants who have a baseline and at least one post-baseline assessment for the endpoint being analyzed will be included in the model. To estimate the difference between the treatment arms in CGI-I and PGIC scores (which do not have baseline assessments), the same method will be used, however, with the observed baseline response and associated interactions removed from the list of covariates. All visits will be included in the analysis. P-values from these comparisons will be considered nominal (conclusions from the sequential testing algorithm will be

reported separately).

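### If the unstructured fit fails, the SAP's fallback covariances force one variance on Weeks 4, 8 and 12, so the Week 12 standard error can be wrong in either direction (low priority)

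*SAP*

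**What the plan says.** SAP 9.1.1 specifies the main choice plainly: "An unstructured covariance matrix will be used to model the within-subject variance-covariance errors". It adds: "The Kenward-Roger approximation will be used to estimate the denominator degrees of freedom". The contingency follows: "Should the unstructured model fail to converge, an autoregressive AR(1) covariance structure will be attempted, then finally compound symmetric should AR(1) not converge". Neither document names a heterogeneous structure, alternative starting values, another algorithm or a robust standard error as a step in between.

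The model covers three post-baseline visits (Weeks 4, 8 and 12), and the primary comparison is at Week 12. For the primary endpoint, missing values are filled in by ten multiple imputations. The SAP does not say whether the fallback is applied to each imputed data set separately or to all ten together, nor whether it is applied stage by stage.

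The rule reaches beyond the primary endpoint. SAP 9.2.1 says the continuous secondary endpoints "will be analyzed using an MMRM model identical to the primary endpoint", but without imputation. That list has 17 endpoints. Two of them, CGI-I and SDS total, are key secondaries in the fixed testing sequence. The MAR supporting model in SAP 9.1.2.3 inherits the rule too.

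**The concern.** An unstructured matrix gives Week 12 its own variance, and that variance drives the standard error of the Week 12 treatment difference. SAP 7.1 states that "All analyses will be performed using Statistical Analysis System". In that software, AR(1) and compound symmetric without further qualification mean the homogeneous forms, with one variance shared by all visits. The fallback therefore discards the feature that matters most for the test. Kenward-Roger accounts for the covariance parameters being estimated within the chosen structure. It does not repair a wrong structure.

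If the residual spread is larger at Week 12 than at Weeks 4 and 8, the shared variance is too small for Week 12, so intervals are too narrow and p-values too low. If the spread is smaller at Week 12, the test is conservative and loses power. One feature of the plan could widen the Week 12 spread: some dropouts are imputed from baseline values (SAP 9.1.1), and dropouts accumulate. The documents do not establish that this happens.

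**Working it through.** **Inputs from the documents.** Three visits. Planned enrolment is "approximately 550 participants total in a 1:1 randomization, that is, 275 participants in each of the placebo and TNX-102 SL 5.6 mg groups" (SAP 5). The default level is that "significance tests of treatment differences will be tested at the two-sided 0.05 level" (Protocol 13). The one-sided level that applies after the interim look is redacted, so 1.96 is used throughout.

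**Inputs assumed.** Residual SDs at Weeks 4/8/12 and correlations of 0.3 to 0.8. The documents give neither.

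**The plan's own figures.** The plan states no standard error or variance for this point, and the sample size cannot be reproduced because its basis is redacted. The stage weights do reproduce: √(275/550) = 0.7071 = √0.5.

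**Step 1: what compound symmetry estimates.** With complete data, its single variance is the mean of the three visit variances. Hence:
- SE ratio (reported/true) = √(mean of the three visit variances / Week 12 variance)
- actual two-sided level = 2 × [1 − Φ(1.96 × ratio)]

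Example with 11/12/13: mean variance = (121 + 144 + 169)/3 = 144.7; ratio = √(144.7/169) = 0.925; level = 2 × [1 − Φ(1.813)] = 7.0%.

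| Assumed SDs, Weeks 4/8/12 | Mean variance | Week 12 variance | SE ratio | Actual level |
|---|---|---|---|---|
| 12/12/12 | 144.0 | 144 | 1.00 | 5.0% |
| 12/12.5/13 | 156.4 | 169 | 0.96 | 5.9% |
| 11/12/13 | 144.7 | 169 | 0.93 | 7.0% |
| 10/12/14 | 146.7 | 196 | 0.87 | 9.0% |
| 9/12/15 | 150.0 | 225 | 0.82 | 11.0% |
| 13/11/9 | 123.7 | 81 | 1.24 | 1.5% |

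**Step 2: AR(1).** AR(1) was fitted by minimising log|V| + tr(V⁻¹S) over its two parameters, where S is the assumed covariance. The result is almost the same. At 9/11/13 the ratio is 0.856 to 0.858 across the correlation patterns, against 0.855 for compound symmetry. At 8/11/14 it is 0.806 to 0.810, against 0.805. The correlation hardly matters.

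**Step 3: absolute size.** At 9/11/13 with 275 per arm, the true SE is √(2 × 169/275) = 1.109. Compound symmetry reports √(2 × 123.7/275) = 0.948.

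**Step 4: does the two-stage combination absorb the error?** Two stages of 274 were simulated at 9/11/13 with equal-weight inverse-normal combination. The rejection rate was 0.0498 for the unstructured fit and 0.0934 for compound symmetry (20,000 trials each), and 0.095 for AR(1) (2,000 trials). The combination does not remove the inflation.

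**Step 5: does a fuller model change this?** A REML fit at 9/11/13 with a mean model like the plan's (20 sites assumed) gave these mean Week 12 SEs:
- no dropout: unstructured 1.120, AR(1) 0.966, compound symmetry 0.965
- 20% dropout: 1.205, 1.020 and 1.013

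The ratios are 0.966/1.120 = 0.86 and 1.020/1.205 = 0.85 for AR(1). These rest on 80 to 90 runs, which is enough for mean SEs but not for rejection rates.

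**The case against.** The strongest reply is that the rule will almost never be used. The unstructured matrix has six parameters, the primary data are completed by imputation, and about 275 participants are planned per stage. Test fits outside SAS, with 45 sites assumed, failed in 0 of 200 runs for a complete continuous total at N = 250. They also failed in 0 of 200 for 0–4 item change scores with 30% dropout at the same N. Zero in 200 still allows a failure rate of up to about 3/200 = 1.5% in those settings, and it does not prove that SAS cannot fail. It does support calling the trigger remote. The unconditional effect is then small. If the fallback occurred in an assumed 1% of trials, 10/12/14 would give 5% + 0.01 × (9.0% − 5.0%) = 5.04%; at 5% of trials it would give 5.2%. This part of the reply stands and sets the priority.

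It is also fair that the rule is ordered and prespecified and is triggered only by non-convergence, so it gives no freedom to choose a favourable result.

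A reader might infer two stronger things that the documents do not support:
- **That CAPS-5 variance grows over the trial, so the fallback is anti-conservative.** No visit SDs are given, and the prior-study summary and the sample-size rationale are redacted. Either direction is possible.
- **That single CAPS-5 items are especially prone to non-convergence and so put error control at risk.** Nothing in the documents shows this, the test fits did not show it, and SAP 7.1.1.1 makes those p-values descriptive only.

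What the reply does not answer is that, once triggered, the rule fixes a standard error that is right only if the visit variances are equal.

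**Conclusion.** The point holds as a conditional one. It needs two things together: the unstructured fit must fail, and the visit variances must differ. Given both, the Week 12 standard error is off by the ratios tabulated above, in a direction that the documents leave open. With moderate assumed growth in SD (11/12/13 to 10/12/14), a nominal 5% test runs at about 7% to 9%. With the reverse pattern 13/11/9 it runs at about 1.5%. If either condition is absent, there is no effect.

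These figures must not be read as the error rate of the planned primary analysis. That analysis uses the unstructured matrix and is unaffected. For formal inference, only the CAPS-5 total, CGI-I and SDS total are at stake.

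The result rests on reading AR(1) and compound symmetric as homogeneous, on the assumed SDs, and on the 1.96 critical value. Priority is low, but the correction is cheap and is best made before unblinding.

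**What to change.** Replace the fallback sentence in SAP 9.1.1 with an ordered rule:

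1. If the unstructured fit does not converge, try other starting values or another fitting algorithm.
2. Then use heterogeneous Toeplitz, heterogeneous AR(1) and heterogeneous compound symmetry, in that order, keeping Kenward-Roger. Each retains its own Week 12 variance, so the SE ratio should return to about 1.00. The unstructured fit, which also has a free Week 12 variance, gave 0.0498 in the simulation; the heterogeneous structures were not simulated separately.
3. As a last resort, use a Week 12 ANCOVA for the imputed primary data. For the unimputed secondary endpoints, use a simple structure with an empirical (sandwich) standard error.
4. Apply one structure to all ten imputations within a stage.

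The cost is a few lines of text and some covariance parameters. With three visits, heterogeneous Toeplitz has five, and heterogeneous AR(1) and compound symmetry have four each, against two for the homogeneous forms and six for unstructured. Heterogeneous Toeplitz is barely simpler than unstructured and may fail with it, which is why the sequence continues. The sandwich last resort cannot be combined with Kenward-Roger, so the SAP should name the degrees-of-freedom method for that step.

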#### **7.1.1 Adjustments for Multiplicity and Other Alpha Control**

##### **7.1.1.1 Multiplicity**

To adjust for multiplicity and to control for overall type I error, a fixed sequence procedure will be applied to key secondary efficacy endpoints. If the primary analysis produces a result that is statistically significant at a given level, the key secondary

endpoints will be tested in an ordered fashion at the same level. If the analysis for a secondary endpoint does not produce a statistically significant result, then the remaining secondary endpoint analyses will automatically be considered non-significant regardless of the p-value produced. In the case of an early stop or increase in sample size, the same methodology/critical value used for the primary endpoint will be applied to the key secondary endpoints for the purposes of the sequential testing.

The order in which the key secondary endpoints, intended for labeling purposes, will be tested is as follows:

- i. CGI-I score after 12 weeks of treatment (as a continuous outcome)
- ii. Change from baseline in the SDS total score after 12 weeks of treatment.

No other adjustments for multiplicity will be made and other p-values displayed in the output will be considered for descriptive summary purposes only and will not be used for formal inference. Additional details regarding statistical analysis for the listed endpoints can be found in [Section 9.2](#).

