#### **7.1.2 Data Handling for Participants Who Discontinue Study Drug or Withdraw from the Study**

Participants who withdraw/drop out from the study will have their ET visit data collected included in the analysis based on the closest visit window (Week 4, 8 or 12). Visit windows will be assigned by splitting the periods between visits at the midpoint between the visits. If more than one record falls within the window, the one closest to the target date will be used in the analysis.

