#### **9.1.2.2 All dropouts as MNAR**

This sensitivity analysis will be a repeat of the primary efficacy analysis, but imputing all dropouts under the MNAR assumption with values based on the baseline distribution.

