#### **9.1.2.3 MAR Mixed Model Repeated Measures**

This analysis will be identical to the primary analysis, but will not include the MI stage described above.

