### **14.3 Appendix 3: Seeds for Imputation:**

The following is the list of seeds to be used for any imputations; they will be used in the order that they appear in the production dataset programming first for primary analyses, then secondaries in the order given in this SAP. In the instance that a sample size increase is needed, the post-interim imputations will use a seed that is 10 greater than the one used on the corresponding pre-interim code. If the list below is insufficient for the number of seeds required, the list will repeat with values 1 greater than those given.

9529179445  
4148794564  
6635287595  
3215648962  
5558675309  
4529575352  
3242564245  
8884574838  
5364925865  
5666852284

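### Ten imputations leave small, avoidable Monte Carlo noise in a valid primary test; at least 100 would remove about two-thirds of its SD at almost no cost

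*SAP*

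**What the plan says.** SAP 9.1.1 handles missing CAPS-5 scores in the mITT population by multiple imputation. Discontinuations for lack of efficacy, loss to follow-up or an adverse event are imputed from the baseline distribution, and all other missing values under MAR. The number of imputations is fixed: "Ten repeats of the imputation will be performed using Markov Chain Monte Carlo (MCMC) assuming non-monotone missing".

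The LS mean difference gives one p-value per stage, and the two are combined by the inverse normal method with each weight equal to sqrt(0.5). The first-stage result also faces a stopping rule: "The study may stop early for success in the case where the critical boundary is crossed (see Section 5.7 of the ISAP"). The primary result opens the gate to the key secondary endpoints (SAP 7.1.1.1): "If the primary analysis produces a result that is statistically significant at a given level", they are then tested in order.

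Other passages set the limits of the issue:
- **Seeds (SAP 14.3).** "The following is the list of seeds to be used for any imputations". There are ten, with a rule for extending the list.
- **Sensitivity analyses.** SAP 9.1.2.2 reads: "This sensitivity analysis will be a repeat of the primary efficacy analysis, but imputing all dropouts under the MNAR assumption". SAP 9.1.2.1 is likewise a repeat of the primary analysis, so both inherit ten imputations.
- **Reference MMRM (SAP 9.1.2.3).** "This analysis will be identical to the primary analysis, but will not include the MI stage described above".
- **Continuous secondary endpoints (SAP 9.2.1).** "there will be no multiple imputation applied".

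**The concern.** With finitely many imputations the pooled estimate and its standard error depend partly on which draws were made. A different, equally legitimate set of seeds would give a slightly different Z. Away from a boundary this is immaterial. Close to one, the draws could help to settle whether the trial stops early, whether the primary test succeeds, and whether the key secondary endpoints are tested at all. Listing the seeds in advance makes the answer repeatable and prevents choosing a seed afterwards, but it does not make ten draws more precise.

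**Working it through.** **Inputs from the documents.** m = 10 (SAP 9.1.1); about 275 participants at the interim out of 550 planned (SAP 4.1); equal stage weights (SAP 9.1.1). The only related figure that can be reproduced is the weight: sqrt(275/550) = 0.7071 = sqrt(0.5), which agrees.

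**Assumed inputs.** FMI, written λ, of 0.06 to 0.20; Rubin pooling; an illustrative threshold of 1.96 with no early stop. As a plausibility check on λ, an illustrative patient-level simulation of one stage (137 per arm, Week 12 ANCOVA in place of the MMRM, half of dropouts imputed from baseline and half under MAR) gave λ of 0.065, 0.11 and 0.15 for assumed dropout of 15%, 25% and 35%.

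**Step 1: noise in the estimate.** In standard-error units, the Monte Carlo SD of the pooled estimate is sqrt(λ/m). For λ = 0.20 and m = 10 this is sqrt(0.02) = 0.141.

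**Step 2: noise in Z.** The between-imputation variance is also estimated from only m draws, and that contribution grows with Z. For one stage:

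SD(Z) ≈ sqrt[ λ/m + (Zλ/2)² × 2/(m−1) ]

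With equal weights and equal stages, the combined variance is 0.5v + 0.5v = v, evaluated at a stage Z of 1.96/√2 = 1.386. For λ = 0.20 and m = 10: 0.0200 + 0.1386² × 0.2222 = 0.0200 + 0.0043 = 0.0243, so the SD is 0.156 (0.155 by simulation).

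| λ | sqrt(λ/m), m=10 | SD(Z), m=10 (simulated) | SD(Z), m=100 (formula) |
|---|---|---|---|
| 0.06 | 0.077 | 0.080 | 0.025 |
| 0.10 | 0.100 | 0.105 | 0.033 |
| 0.17 | 0.130 | 0.141 | 0.045 |
| 0.20 | 0.141 | 0.155 | 0.049 |

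Moving from 10 to 100 removes 1 − 0.049/0.155 = 68% of the SD at λ = 0.20. In p-value terms, a result whose noise-free Z is 1.96 has a central 95% range of two-sided p over seeds of 0.032 to 0.082 at λ = 0.10 with m = 10, and 0.044 to 0.059 with m = 100 (200 complete-data df assumed).

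**Step 3: consequences.** Two-stage simulation with 1,000,000 trials per setting. Within-imputation variance is 1−λ and between-imputation variance λ, with Barnard-Rubin df from 270 complete-data df and inverse-normal combination. The reference is unlimited imputations on the same data. Columns are for λ = 0.06 / 0.10 / 0.17 / 0.20.

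| Quantity | m=10 | m=100 |
|---|---|---|
| Verdict differs from reference, 80% power | 1.8 / 2.5 / 3.4 / 3.8% | 0.6 / 0.8 / 1.0 / 1.1% |
| Verdict differs, 90% power | 1.2 / 1.6 / 2.2 / 2.5% | 0.4 / 0.5 / 0.7 / 0.7% |
| Verdict differs, null | 0.4 / 0.5 / 0.7 / 0.8% | 0.1 / 0.2 / 0.2 / 0.2% |
| Power, nominal 80% (reference 79.8 / 79.8 / 79.7 / 79.7%) | 79.5 / 79.3 / 78.8 / 78.7% | 79.8 / 79.7 / 79.6 / 79.6% |

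The power loss at m = 10 is thus about 0.3 to 1.1 points before rounding. One-sided type I error at m = 10 is 2.46 / 2.43 / 2.45 / 2.46%, the same as with unlimited imputations.

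**Step 4: imputations needed.**

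| Limit | λ=0.06 | 0.10 | 0.17 | 0.20 | 0.25 |
|---|---|---|---|---|---|
| Monte Carlo error of the estimate ≤ 5% of its SE: m = λ/0.05² = λ/0.0025 | 24 | 40 | 68 | 80 | 100 |
| SD(Z) ≤ 0.05 near Z = 1.96 (Step 2 formula) | 26 | 44 | 80 | 96 | 125 |

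The two limits differ: the first row's m gives SD(Z) of about 0.051 to 0.054 for λ of 0.06 to 0.20, and 0.055 at 0.25. Ten imputations meet the first limit only up to λ = 10 × 0.0025 = 0.025.

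**The case against.** The strongest reply is that nothing here is invalid. The number of imputations and the seeds are fixed in advance, no passage contradicts another, and Rubin's rules charge for finite m. All of that stands. A reader might infer that ten imputations inflate type I error, or leave room to choose a favourable draw. The documents support neither: the seed list closes off selection, and the calculation shows error at nominal.

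A reader might also take the 1.8 to 3.8% as wrong verdicts. They are not. Both versions are valid tests, the differences go in both directions, and the net cost is the power loss. Nor does the noise reach the key secondary tests themselves, which use no imputation; it reaches them only through the gate.

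Missing data are also limited. Protocol 10.5.1 collects CAPS-5 at early termination from Day 11, and SAP 7.1.2 assigns those scores to visits: "Visit windows will be assigned by splitting the periods between visits at the midpoint between the visits". The mITT definition (SAP 6) leaves out anyone with no post-baseline CAPS-5, so such participants are never imputed. These points favour the low end of the FMI range, but even at 0.06 the SD of Z is about 0.08.

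The size cannot be confirmed from the documents. The ISAP and the simulation report are not available and may address imputation precision. The model is also idealised: it does not reproduce the SAP's draws from the pooled baseline values of both arms, so the type I figure is not a calculation for the SAP's exact procedure.

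Finally, the reference MMRM is free of this noise, but it makes a different missing-data assumption and cannot stand in for the primary test.

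**Conclusion.** Minor: a nearly free improvement and not an error in the plan. That ten imputations leave some Monte Carlo noise in the primary statistic is certain. How much is conditional on FMI of 0.06 to 0.20, Rubin pooling and an illustrative 1.96 threshold. On those terms the noise costs about one point of power at most and could matter only for a result close to a boundary. With 100 imputations about two-thirds of the SD disappears, and the power loss falls to about 0.1 point or less.

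**What to change.** Before any unblinded analysis, change the number in SAP 9.1.1 from ten to at least 100, for the interim, both stages and the sensitivity analyses in 9.1.2.1 and 9.1.2.2. State the pooling rule, and report the Monte Carlo error of the pooled estimate. If the ISAP sets its own number of imputations, align it.

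If a precision limit is also stated, say which quantity it governs. A limit of 5% of the standard error on the pooled estimate is met by m = 100 up to FMI 0.25. A limit of 0.05 on SD(Z) near the boundary is met by m = 100 only up to FMI of about 0.20.

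The cost is computing time and a coordinated edit. SAP 4.1 says that the ISAP, IDMC charter and simulation report go to the FDA together with the SAP, and a separate group runs the interim, so the documents must agree. The seed list already has an extension rule. Data collection, estimand, boundaries and sample size do not change.
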